4.3 Primary and secondary outcome measures

4.3.1 Primary

Number of ICU patients with delirium intervened with haloperidol (N05AD01)

(Definition: Patients receiving one or more doses of haloperidol and are described as delirious. Delirium defined as below in secondary outcome 2).

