4.3.2 Secondary

1. Number of ICU patients with delirium intervened with other antipsychotics than haloperidol
(Definition: Patients receiving one or more doses of 2nd generation anti-psychotics² including olanzapin (N05AH03), rivastigmin (N06DA03), risperidon (N05AX08) and quetiapine (N05AH04),

¹ Denmark, Norway, Sweden, Finland, Netherland, Switzerland, Germany, United Kingdom, Belgium, Spain, Italy, Canada, Brazil and France

AND described as delirious (see definition in secondary outcome 2. Number of patient with delirium)

2. Number of patients with delirium

(Definitions: ICU documented CAM-ICU positive or ICDSC ≥ 4 points (0-8 points) or DOS >3 points (0-13/day points), ICD-10 code (DF05, DF050, DF05), or agitated and/or non-cooperative and/or eyes open wide with no contact (Glasgow Coma Score (GCS) > 7) or restrained to the bed).

3. Mortality at 90 days

(Definition: Death within 90 days of ICU admission)

4. Days alive in ICU without coma and/or delirium

(Definition Coma: Number of calendar days the patient is alive without coma in the period from ICU admission to discharge. Coma defined as RASS (Richmond Agitation Sedation Score) score -3 to -5, Ramsey sedation score 4 to 6, MASS (Motor Activity assessment Scale) 1 to 0 and GCS < 8 . Delirium Definition: Number of calendar days the patient is alive without delirium in the period from ICU admission to discharge. Delirium defined as above in secondary outcome 2. All assessments in a 24 hour period need to be negative for a patient to be assessed delirium-free).

5. Days alive without mechanical ventilation and days alive out of hospital (ICU) in a 90-day period

(Definition: Patient treated with mechanical ventilation either endotracheal intubated or tracheostomy, on controlled or spontaneous mode or patient treated with continuous non-invasive ventilation (NIV) for more than 1 hour. Number of days without a ventilator is registered every 24 hours; every new day at 6 AM is registered as one day. If a patient is re-intubated/or started NIV within 24 hours it will be registered as a full day of mechanical ventilation.

Definition: Number of days alive after discharge from the hospital (ICU), the day of discharge do not count, but from the next day at 6 AM).

6. Rate of cognitive impairment at 6 months after ICU discharge (only in Denmark)

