6.1 Patient evaluation

Baseline patient characteristics

1. Age on the day of ICU admission (years)

2. Gender (male/female)
3. Simplified Acute Physiology Score II (SAPS II) within the first 24 hours of the ICU admission (0-163 points)
4. Use of dialysis, vasopressors or inotropes (noradrenaline (C01CA03), adrenaline (C01CA24), dobutamine (C01CA07), dopamine (C01CA04), milrinone (C01CE02), levosimendan (C01CX08) vasopressin (H01BA01) or phenylephrine (C01C A06) and/or medical ventilation (y/n)
5. Days admitted in the hospital prior to ICU admission (number of days)
6. Type of admission diagnose (sepsis y/n, trauma y/n, surgery 24 hour prior to admission y/n, elective surgery y/n, emergency surgery y/n)
7. Treatment with antipsychotics (N05A), anti-Parkinson (N04), antidepressant (N06A) and benzodiazepine (N05BA) prior to hospital/ICU admission
8. Risk factor status prior to hospital/ICU (*Previous delirious episodes defined as: patients receiving one or more doses of haloperidol, AND described as delirious (documented CAM-ICU positive or ICDSC ≥ 4 point (0-8 point) or DOS >3 point (0-13/day point), ICD-10 code (DF05, DF050, DF058), or agitated and/or not cooperative and/or eyes open and big with no contact (Glasgow Coma Score (GCS) > 7) and/or anxiety, or restrained to the bed), smoking more than 10 cigarettes a day yes/no, alcohol abuse more than 3 units (1 units defined as 12 g of alcohol) a day yes/no)*)
9. Hearing or vision impairment (y/n)

Daily data collection from admission through last day of follow-up (discharge from ICU or day 90

10. Sedation assessment (the sites will only register the score (a, b or c) they use in clinical practice), as described in patient files, one score equals one positive day with sedative induced coma.
 - a. RASS score -3- (-5) (y/n) at any time during the day or
 - b. Ramsey sedations score 4-6 points (y/n) at any time during the day or
 - c. MASS score 1-0 (y/n) at any time during the day
11. Coma assessment, as Glasgow Coma Scale (GCS) score without any sedation
 - a. GCS < 8 point (y/n) at any time during the day
12. Delirium assessment (the sites will only register the score (a, b or c) they use in clinical practice), as described in patient files, one positive score equals one delirium day. (appendix 2)
 - a. CAM-ICU (positive /negative/UTA, Unable To Assess)
 - b. ICDSC ≥ 4 point (0-8 point)
 - c. DOS >3 point (0-13 point)
 - d. ICD 10 code DF05, DF050, DF058

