6.2 Unit/department evaluation

24. Type of hospital (< 500 beds/500-1000 beds/ > 1000 beds)
25. Type of ICU (Medical/Surgical/Mixed/Specialised)
26. Number of ICU beds open for admission
27. Does your ICU have a general guideline/protocol for identifying delirium?
28. Does your ICU have a general guideline/protocol for interventions of delirium?
29. When do you intervene for delirium?
30. Are patient restrained in your ICU (never, sometimes, often)?
31. Average nurse to patient ratio during the day, evenings and nights.

7. Statistical Methods

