7. Sleep wake/cycle disturbance	"1" for any of the following: 
 Sleeping less than 4 hours or waking frequently at night (do not consider wakefulness initiated by medical staff or loud environment) Sleeping during most of day 	
8. Symptom fluctuation	"1" for fluctuation of the manifestation of any item or symptom over 24 hours (e.g., from one shift to another)	
TOTAL SCORE 0-8 / 8	A score ≥ 4 suggests delirium. A score > 4 is not indicative of the severity of the delirium	

Delirium Observation Screening (Dos) Scale (version 0 - 1)

Date:
Patient Name:

OBSERVATION	The patient	Day shift			Evening shift			Night shift			TOTAL SCORE TODAY (0 - 39)
		Never	sometimes - always	unable	never	sometimes - always	unable	never	sometimes - always	unable	
1	Dozes off during conversation or activities	0	1	-	0	1	-	0	1	-	
2	Is easily distracted by stimuli from the environment	0	1	-	0	1	-	0	1	-	
3	Maintains attention to conversation or action	1	0	-	1	0	-	1	0	-	
4	Does not finish question or answer	0	1	-	0	1	-	0	1	-	
5	Gives answers that do not fit the question	0	1	-	0	1	-	0	1	-	
6	Reacts slowly to instructions	0	1	-	0	1	-	0	1	-	
7	Thinks they are somewhere else	0	1	-	0	1	-	0	1	-	
8	Knows which part of the day it is	1	0	-	1	0	-	1	0	-	
9	Remembers recent events	1	0	-	1	0	-	1	0	-	
10	Is picking, disorderly, restless	0	1	-	0	1	-	0	1	-	
11	Pulls IV tubing, feeding tubes, catheters etc.	0	1	-	0	1	-	0	1	-	
12	Is easily or suddenly emotional	0	1	-	0	1	-	0	1	-	
13	Sees/hears things which are not there	0	1	-	0	1	-	0	1	-	
TOTAL SCORE PER SHIFT (0 - 13)											
DOS SCALE FINAL SCORE = TOTAL SCORE TODAY / 3											

DOS SCALE Final Score	< 3	Not delirious
	≥ 3	Probably delirious

**Table 1. The Glasgow Coma Scale
And The Glasgow Outcome Scale.**

Glasgow Coma Scale

Eye opening

Spontaneous	4
To speech	3
To pain	2
No response	1

Verbal response

Alert and oriented	5
Disoriented	4
Speaking but nonsensical	3
Moans	2
No response	1

Motor response

Follows commands	6
Localizes pain	5
Withdraws to pain	4
Decorticate flexion	3
Decerebrate extension	2
No response	1

Grading of TBI:*

Mild†	13-15
Moderate	9-12
Severe	3-8

* A single GCS score is neither diagnostic of TBI nor predictive of outcome.

† Because of the 10% or greater incidence of craniotomy in these patients, many authorities now consider a GCS of 13 to represent moderate brain injury.

Glasgow Outcome Score

D	=	Dead
PVS	=	Persistent vegetative state
SD	=	Severe disability

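### The delirium definition behind the primary outcome conflicts with its own appended DOS scale and includes behavioural signs that the listed daily data do not capture

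*Protocol*

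**What the plan says.** Protocol section 4.3.1 defines the primary outcome as patients given haloperidol at least once and described as delirious, and states "Delirium defined as below in secondary outcome 2". Secondary outcomes 1 and 4 refer to the same definition, and secondary outcome 2 is the delirium count itself.

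The definition in section 4.3.2 has three parts:

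- A screening tool: "ICU documented CAM-ICU positive or ICDSC ≥ 4 points (0-8 points) or DOS >3 points (0-13/day points".
- An ICD-10 delirium code.
- Behaviour or restraint: "or agitated and/or non-cooperative and/or eyes open wide with no contact (Glasgow Coma Score (GCS) > 7) or restrained to the bed".

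In section 6.1, daily item 12 reads "Delirium assessment (the sites will only register the score (a, b or c) they use in clinical practice". Its DOS line (12c) is "DOS >3 point (0-13 point", and baseline item 8 (previous delirious episodes) uses the same cut-off. The DOS form in Appendix 3 divides the day's total (0 to 39) by 3. It labels a final score below 3 as not delirious and a score of 3 or more as "Probably delirious".

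**The concern.** An outcome definition has to agree with the instrument it cites, and each of its criteria needs a data source. This one fails on both counts.

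On the DOS cut-off, a nurse following the appended form and a data collector following section 4.3.2 would classify the same boundary day differently. On the behavioural signs, a patient can be delirious by definition while none of the listed daily items shows it. The primary outcome and secondary outcomes 1, 2 and 4 are all affected. An analysis plan written later could choose between cut-offs if raw scores are kept, but it could not restore daily observations that were never collected.

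**Working it through.** **Step 1. Match each criterion to its daily source** (section 4.3.2, outcome 2, against section 6.1, items 10-19).

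| Criterion | Daily source |
|---|---|
| CAM-ICU positive | item 12a |
| ICDSC of 4 or more | item 12b |
| DOS above 3 | item 12c (conflicts with Appendix 3) |
| ICD-10 code | item 12d |
| Agitation, non-cooperation, or eyes open without contact, GCS above 7 | none |
| Restraint | item 14 |

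Item 11 records only whether GCS was below 8. Item 13 records the motor subtype, which describes delirium already identified. In section 6.1 the behavioural signs appear only in baseline item 8, as part of the definition of earlier episodes, and there with anxiety added. In an ICU that uses no screening tool, the listed data therefore leave only an ICD-10 code or restraint to establish delirium.

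**Step 2. Compare the DOS rules.** Final score = daily total / 3, with totals from 0 to 39.

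| Total | Final score | Section 4.3.2 (>3) | Appendix 3 (≥3) |
|---|---|---|---|
| 8 | 2.67 | no | no |
| 9 | 3.00 | no | yes |
| 10 | 3.33 | yes | yes |

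Of the 40 possible totals, only 9 is classified differently. If sites round the final score to a whole number (an assumption; the protocol does not say), totals 8, 9 and 10 all become 3 and all three are classified differently. Both rules are stated on a 0-13 score, so a difference of scale does not explain the conflict.

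**Step 3. Reproduce the planned precision** (section 7.1: 13%, 1000 patients, 95% interval 11%-15%).

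Half-width = 1.96 × √(0.13 × 0.87 / 1000) = 0.0208, giving 10.9% to 15.1%. The stated interval is reproduced.

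**Step 4. Show what an undercount would do.** The protocol gives no figure for the share *m* of true primary-outcome cases that qualify by the unrecorded signs alone, so *m* is an assumption. Observed rate = 13% × (1 − *m*).

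| *m* | Observed rate |
|---|---|
| 5% | 12.4% |
| 10% | 11.7% |
| 20% | 10.4% |
| 30% | 9.1% |

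The shift equals the planned half-width when 13 × *m* = 2.08 points, that is at *m* = 16%. This is a yardstick and not an estimate of *m*.

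**The case against.** **The case report form is not shown.** Section 6.1 is a list of variables, and the electronic form might hold more. That is a fair limit, and the point is confined to the listed data. Still, section 6.1 goes down to individual hypnotics, and these signs are absent from it.

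**Other items might stand in.** Item 19 records drugs given as an intervention for delirium, with a prophylaxis flag, and item 13 records subtype. They help but do not replace the missing signs. Item 19 shows that a drug was given, not that the patient met the definition. Using it as proof of delirium would let treatment define the condition, and untreated patients would still be missing from secondary outcome 2.

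**The DOS conflict is small.** This stands. Outcomes that count patients change only where someone at a DOS site reaches exactly 3, never more, and meets no other criterion. Secondary outcome 4 counts days, so there each boundary day without another positive criterion matters.

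**Reliance on site practice is deliberate.** This also stands. The study describes current practice, and letting each site use its own tool is a design choice with a known limitation.

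A reader might go on to infer two stronger points, which the protocol does not support:

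- *That having a delirium guideline would be tied to the outcome by construction.* In section 7.3 the model with that covariate is for use of haloperidol, which item 19 records whether or not the patient is classed as delirious. The mortality model lists no ICU characteristics.
- *That restraint should not count as delirium because the unit questionnaire asks "Are patient restrained in your ICU (never, sometimes, often".* That question adds unit-level context. Restraint is stated openly as a criterion, is recorded per patient in item 14, and can be separated at analysis.

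**Conclusion.** The point holds for two defects: one definition carries two DOS cut-offs, and one of its criteria has no daily data source in section 6.1. The second matters more, because it leaves the primary outcome not fully computable as defined. Missed patients would come mainly from ICUs that use no screening tool, and the count of delirious patients would be too low.

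The size is unknown. The protocol does not say how many sites use DOS or no tool, or how many patients show only behavioural signs. A figure built on a guessed share of ICUs without a tool would only restate the guess. The 16% benchmark rests on the protocol's 13% and 1000 patients, and on the assumption that the 13% reflects the full definition. The conclusion also assumes that the electronic form follows the section 6.1 list.

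**What to change.** 1. Reconcile the DOS cut-off across section 4.3.2, items 8 and 12c, and Appendix 3 so that one study threshold applies. The appended instrument's own is "≥ 3 Probably delirious"; if the study means to depart from it, the protocol should say so. State whether the final score is rounded.
2. Before inclusion starts, either add one daily yes/no item for the behavioural criterion with GCS above 7, or delete that criterion from the definition. If it stays, align the wording in item 8, which adds anxiety.
3. Optional: a sensitivity analysis showing cases that qualify by restraint or behaviour alone separately from those confirmed by a tool or ICD-10 code.

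The cost is a few wording edits, at most one form field and a small added data-entry burden. Deleting the criterion avoids that burden but narrows the definition.

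### The protocol's DOS cut-off for delirium (above 3) disagrees with the DOS form it appends (3 or above) at a final score of exactly 3.0

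*Protocol*

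**What the plan says.** Section 4.3.2, outcome 2, lists several alternative routes to a delirium classification. The DOS route is "DOS >3 points (0-13/day points". Section 6.1 gives the same cut twice: in item 8, within the definition of previous delirious episodes ("DOS >3 point (0-13/day point"), and in item 12c, the daily assessment ("DOS >3 point (0-13 point").

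The DOS form in Appendix 3 scores three shifts, each with "TOTAL SCORE PER SHIFT (0 - 13") as its range, and sums them to a day total of 0 to 39. It then sets "DOS SCALE FINAL SCORE = TOTAL SCORE TODAY / 3". A final score below 3 is labelled not delirious; 3 or above is labelled "Probably delirious".

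Section 4.3.1 ties the primary outcome to this definition: "Delirium defined as below in secondary outcome 2". Outcomes 1 and 4 in section 4.3.2 refer to it too. For outcome 4 the rule is strict: "All assessments in a 24 hour period need to be negative for a patient to be assessed delirium-free".

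**The concern.** The body and the appendix use the same instrument on the same 0-13 daily range, so a difference of units does not explain the different cuts. A single typing slip is also unlikely: the stricter symbol appears three times, and in the same sentence of outcome 2 the ICDSC cut is written as 4 or above, which agrees with the appended ICDSC form.

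The protocol therefore holds two rules for one case definition. Section 6.1 has sites take the assessment from patient files. A site whose chart follows the form's label and a site that applies the protocol's cut could classify the same day differently. The definition enters the numerator of the primary outcome, outcomes 1, 2 and 4, and, as delirium in the first 24 hours, the covariate list of both multivariate analyses in section 7.3. Because sites register only the scale they use in practice, the discrepancy would arise at DOS sites and not at ICDSC or CAM-ICU sites.

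**Working it through.** **Inputs.** Trial rule: DOS above 3 on 0-13 (sections 4.3.2 and 6.1). Form rule: final score 3 or above, with final score = day total / 3 and day total from 0 to 39 (Appendix 3).

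**Step 1: convert both rules to day totals.**
- Form: total / 3 ≥ 3, so positive from a total of 9.
- Trial: total / 3 > 3, so positive from a total of 10 (10 / 3 = 3.33).

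**Step 2: find the disagreement.** Of the 40 possible totals (0 to 39), only 9 is classed differently, a final score of exactly 3.0. Neighbouring scores agree: 8 / 3 = 2.67 is negative under both rules and 10 / 3 = 3.33 is positive under both.

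**Step 3: what it takes to lose a patient.** Outcome 2 joins its routes with *or*. A day at 3.0 still counts if the patient has the ICD-10 code, is agitated or non-cooperative or has open eyes without contact, or is restrained. A haloperidol-treated patient leaves the primary numerator only if no DOS score in the stay exceeds 3, at least one equals 3.0, and none of the other routes is ever met.

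**Step 4: does the unit of scoring matter?** Item 12c omits the words that mark the score as daily, and the form also gives a 0-13 score per shift. Suppose each shift score were tested against the cut of above 3:
- 55 combinations of three shift scores add up to 9. All but one (3+3+3) contain a shift of 4 or more, so 54 of 55 would be positive in the trial.
- A day of 4+0+0 has a final score of 4 / 3 = 1.33. It would be positive in the trial and negative on the form.

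On this reading the discrepancy largely runs the other way. Outcome 2 and item 8 do mark the score as daily, which favours the daily reading, but the protocol should say so wherever the cut appears.

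**Step 5: can the size be derived?** No. The protocol gives no distribution of DOS scores and no number of DOS sites. Purely as assumptions: if form-positive totals were spread evenly over 9 to 39, the share at exactly 9 would be 1 / 31 = 3.2%. With negative binomial totals it would be 4.9% (mean 18, dispersion 4) to 19.2% (mean 6, dispersion 2). These are shares of DOS-positive days, before the other routes are taken into account. The primary outcome and outcomes 1 and 2 count patients, for whom one positive day is enough, so these shares are not estimates of the effect on those outcomes.

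**The case against.** The strongest reply is that this is one score value, in one of several alternative criteria, at an unknown subset of sites. A patient given haloperidol for delirium will often be agitated or non-cooperative and would be counted anyway. That stands, and it limits the weight of the point.

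It can also be said that the form's label is a screening label and that the sponsor may have meant a stricter cut, since the body uses it consistently. That cannot be excluded. But the protocol gives no reason for departing from the form it appends, so the two places still have to be reconciled.

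A reader might infer more than the protocol supports:
- *Days scoring 3 are delirium-free in the trial.* This holds on the DOS criterion alone; the other routes can still make the day count.
- *A sizeable share of delirium is lost, more so if 3.33 and 3.67 are cut down to 3.* The form divides by 3 and gives no rounding instruction, so truncation is not supported, and the shares in the working are assumptions at day level.
- *Sites fill in the appended form, and the eCRF stores only yes or no.* The protocol states neither. Appendix 3 presents assessment tools, section 6.1 refers to what patient files record, and the eCRF is not shown. Items 10 and 11 are marked as yes/no, whereas 12c gives a score range, so a numeric entry may already be intended.
- *The cut creates an artificial difference between sites.* It could contribute to one, but sites already use different tools, and the protocol does not allow this part to be separated.

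**Conclusion.** The contradiction is real and lies in a case definition that the primary outcome uses. On the daily reading, the rules disagree only at a final score of exactly 3.0 (day total 9 of 39), which the form calls positive and the trial's DOS criterion calls negative. The day is lost from the delirium count, and any haloperidol from the primary numerator, only where no other criterion is met. The effect is confined to DOS sites, is probably small, and cannot be quantified from the protocol. The conclusion rests on reading the cut as applying to the unrounded daily final score; on a per-shift reading the direction is different. Severity is minor to moderate: worth correcting because the definition is central and the correction is cheap, not because a large bias has been shown.

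**What to change.** Reconcile outcome 2 in section 4.3.2, items 8 and 12c in section 6.1, and the form in Appendix 3 to one DOS cut-off. The appended form's 3 or above is the natural default. If a stricter cut is intended, keep it, give the reason, and note in the appendix that the trial departs from the form's label. State in each place that the cut applies to the daily final score, day total divided by 3, without rounding.

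Record that score as a number with decimals, if the eCRF does not already do so, and derive the classification centrally. Either cut can then be applied in the analysis and days at exactly 3.0 can be counted.

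The cost is a change of symbol and a short clarification in three places (or a reason and a note if the stricter cut is kept), and at most one numeric eCRF field. Sample size, schedule and analysis methods do not change.

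### The delirium definition behind the primary outcome has a behaviour-only criterion that the daily data list does not collect

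*Protocol*

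**What the plan says.** Section 4.3.1 defines the primary outcome by two conditions: "Patients receiving one or more doses of haloperidol and are described as delirious. Delirium defined as below in secondary outcome 2".

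Outcome 2 in section 4.3.2 then offers several routes to delirium joined by 'or', so each is sufficient alone:

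- a positive tool: "ICU documented CAM-ICU positive or ICDSC ≥ 4 points (0-8 points) or DOS >3 points (0-13/day points";
- an ICD-10 code;
- described behaviour: "agitated and/or non-cooperative and/or eyes open wide with no contact (Glasgow Coma Score (GCS) > 7";
- restraint to the bed.

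Secondary outcome 1 (other antipsychotics) and secondary outcome 4 (days without coma and/or delirium) refer back to this definition.

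Section 6.1 lists what is collected each day. Item 12 takes the score of whichever tool the site uses (12a to 12c) and the code (12d), with the counting rule "one positive score equals one delirium day". Item 13 is the delirium subtype and item 14 is restraint.

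**The concern.** The definition and the data list do not match. A criterion that is enough by itself to make a patient delirious has no daily item to record it. A later analysis plan can decide how to combine variables, but it cannot derive one that was never collected.

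The primary outcome requires both haloperidol and delirium. A treated patient whose delirium is documented only as agitation, non-cooperation or open eyes without contact meets the definition but may not be identifiable in the data. The gap is likely to be wider at a site that uses no tool, because there only the code and restraint remain as recorded routes. Part of any difference between sites could then reflect how delirium is documented rather than how haloperidol is used.

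**Working it through.** **Step 1. Match each route in section 4.3.2 to the daily items in section 6.1.**

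| Route in 4.3.2 | Daily item in 6.1 |
|---|---|
| CAM-ICU, ICDSC or DOS | 12a, 12b, 12c (only the site's own tool) |
| ICD-10 code | 12d |
| Agitated, non-cooperative, or no contact | none |
| Restraint | 14 |

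**Step 2. Check the near-matches.**

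- Item 11 records GCS below 8 (yes/no) without sedation. It can inform the GCS qualifier but says nothing about behaviour.
- Item 13 classifies delirium as hypoactive, hyperactive or mixed. It is not a yes/no record of agitation, and it has no category for non-cooperation or lack of contact.
- The ICDSC and DOS forms in Appendix 3 contain agitation-type items. These count only through the tool's total, and only where that tool is used.
- Item 8 contains the behavioural wording, but it is a baseline item about previous episodes. It also requires haloperidol and adds anxiety to the list.
- Item 19 records drugs given for delirium, not the behaviour that led to them.

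None of these records the behavioural criterion during the stay.

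**Step 3. Reproduce the planned precision.** Section 7.1 assumes a rate of 13% with 1000 patients:

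0.13 ± 1.96 × √(0.13 × 0.87 / 1000) = 0.13 ± 0.021, that is 10.9% to 15.1%.

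This agrees with the stated 11% to 15%.

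**Step 4. Illustrate the possible loss.** Let q be the share of haloperidol-treated delirious patients who qualify by behaviour alone and are missed. The documents do not give q, so the values below are assumptions. Observed rate = 13% × (1 − q), with the same interval formula at n = 1000.

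| q (assumed) | Missed of 130 | Observed rate | 95% interval |
|---|---|---|---|
| 10% | 13 | 11.7% | 9.7% to 13.7% |
| 20% | 26 | 10.4% | 8.5% to 12.3% |
| 30% | 39 | 9.1% | 7.3% to 10.9% |

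The estimate falls to 11%, the lower end of the planned interval, at q = 1 − 0.11/0.13 = 15.4%. That interval is a statement of precision, not an acceptance range, so crossing it shows scale and nothing more.

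**The case against.** The best reply is that a treated, agitated patient leaves other traces. Item 19 records haloperidol as an intervention for delirium, with a flag for prophylaxis, and item 13 is not expressly conditional on a positive item 12. Such a patient might be recovered from these items even without a code or restraint. This stands in part: it is too strong to say that a patient without a tool score can be counted only if coded or restrained. But neither item records the behaviours, and inferring delirium from the drug would make the primary outcome partly circular. For untreated patients in outcome 2, item 19 gives no trace of haloperidol at all.

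It is also fair to say that the eCRF and the figures of Appendices 1 and 2 are not shown, so an extra field could exist. The visible appendix labels do not suggest one, and section 6.1 is the protocol's own list of data items. If the field exists, the protocol text still needs the line.

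Several stronger readings are tempting and are not supported:

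- **Affected days are scored as delirium-free.** Section 4.3.2 says "All assessments in a 24 hour period need to be negative for a patient to be assessed delirium-free". A day with no tool assessment is unassessed rather than clearly negative, and its handling may be left to an analysis plan. Outcome 4 shares the incomplete definition, but the direction of its error on such days is not established.
- **ICUs without a tool are expected.** Section 6.2 asks "Does your ICU have a general guideline/protocol for identifying delirium". That concerns a guideline and does not show that any site will lack a screening tool.
- **The GCS qualifier is unusable under sedation.** Item 11 reads "Coma assessment, as Glasgow Coma Scale (GCS) score without any sedation", and item 10 covers sedation separately, which looks deliberate. The qualifier in section 4.3.2 may also attach only to the no-contact behaviour. Asking for GCS on sedated days would be a preference, not a correction.
- **The ICD-10 lists conflict in substance.** Item 12 has "d. ICD 10 code DF05, DF050, DF058", while section 4.3.2 repeats DF05 in the third place. This looks like a typing slip.

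**Conclusion.** The mismatch is real and can be seen within the protocol. Behaviour alone is sufficient for delirium in section 4.3.2, section 4.3.1 carries that into the primary outcome, and the daily list in section 6.1 does not collect it. Patients who qualify only by this route can be missed from the delirium count and from the primary numerator, with secondary outcome 1 exposed in the same way.

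A reader might infer that the primary outcome cannot be derived at all. The documents do not support that: the tool, code and restraint routes are all recorded, and items 13 and 19 may give a partial trace. What cannot be derived from the listed items is the outcome exactly as defined.

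The size is unknown. The range of 11.7% to 9.1% rests on an assumed q of 10% to 30%, on none of those patients being recovered by other means, and on the 13% having been obtained with the behavioural route included. Section 7.1 takes that 13% from one department's preliminary data and does not state the delirium definition used, so the last assumption cannot be checked. The planned frequency of haloperidol use as such in section 7.3 does not depend on the delirium definition and is unaffected.

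**What to change.** Choose one of two changes so that sections 4.3.2 and 6.1 agree.

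1. Add a daily yes/no item 12e for the behavioural criterion, worded as in section 4.3.2, and extend the counting rule in item 12 to cover it. Report the primary outcome in total, and split into patients positive by tool, code or restraint and patients positive by behaviour only. The split shows how much of the result rests on described behaviour.
2. If the item will not be collected, delete the behavioural criterion from section 4.3.2, so that the primary outcome and secondary outcomes 1, 2 and 4 rest on what is recorded.

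The first option costs one more field per patient-day, read from charts already in use, with no extra patients or procedures. The second costs only a wording change but narrows the definition. In the same edit, align the ICD-10 list in section 4.3.2 with item 12d as a clerical tidy-up.
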